| [name] (oral reviewer) |
| |
| |
| - [name] |
| |
| |

Abbreviations

CI Confidence interval

EC Ethics Committee

EORTC European Organisation for Research and Treatment of Cancer

LMM Linear Mixed model

MAR Missing At Random

MNAR Missing Not At Random

REDCap Research Electronic Data Capture

REML Restricted Maximum Likelihood

SAP Statistical Analysis Plan

QL Quality of Life

Introduction

Background and rationale

Contemporary cancer care for older populations needs an innovative, effective, and cost-effective concept or approach to sustainably meet the increasing demand for high-quality, supportive, palliative, and end-of-life care within existing EU healthcare systems.

Navigation interventions or programs hold promise to meet these needs. Scientific evidence for patient and family navigation mainly comes from the US and Canada and suggests favourable feasibility and effectiveness, and promising results of cost-effectiveness for patient navigation in cancer care, specifically during the beginning phases of illness, i.e. cancer screening and diagnosis, and more recently in improving cancer treatment and care (Bernardo et al, 2019; Roland et al, 2017). Evidence for its use in supportive, palliative, end-of-life care is much weaker (72% of studies of navigation program in cancer focused on the early phases) and particularly in older cancer populations (Bernardo et al, 2017; van Ee et al, 2017).

The Canadian Nav-Care[©] programme is a person- and family-centered navigation intervention. It has potential to improve quality of life and wellbeing for older cancer patients and their family caregivers. Nevertheless, high-quality research designs such as pragmatic randomized controlled trials or studies using a control group have not been used to evaluate Nav-Care. In addition, it needs yet to be adapted and evaluated in European health care systems, using high-quality research designs and measurements.

Objectives

The primary objectives are to evaluate the effectiveness of the NavCare-EU intervention compared with care as usual for improving global health status / quality of life and level of social support in older persons with cancer living at home.

A secondary objective is to evaluate the effectiveness of the NavCare-EU intervention compared with care as usual for reducing caregiver burden in close family caregivers of older persons with cancer living at home.

Exploratory objectives are to explore the uniformity of the intervention effect compared with care as usual across

- different subgroups defined by baseline characteristics known to affect health equity and equitable access
- different health care systems and care regimens in Europe.

Endpoints

Primary endpoints

- Change from baseline at 24 weeks in global health status/quality of life as measured by the 2-item subscale from the EORTC QLQ-C30 (version 3.0) in older persons with cancer
- Change from baseline at 24 weeks in levels of social support (i.e. emotional/informational support, tangible/instrumental support, positive social interaction, and affection) as measured by the Medical Outcomes Study Social Support Survey in older persons with cancer

Secondary endpoints

- Change from baseline at 24 weeks in feelings of loneliness as measured by the 3-item-UCLA Revised Loneliness Scale in older persons with cancer
- Change from baseline at 24 weeks in Caregiver burden as measured by the Zarit Burden Interview Short Form in close family caregivers of older persons with cancer

Exploratory endpoints

Change from baseline at 24 weeks in:

- Symptoms or problems experienced (i.e. as measured by the symptom scales/items and the emotional functioning scale from the EORTC QLQ-C30 (v 3.0) in older persons with cancer
- Well-being of older people as measured by the Well-Being of Older People measure (WOOP), which captures a comprehensive set of well-being domains relevant to older people (broader than health)
- Knowledge of resources and services and confidence in decision-making, as measured by the Items from Patient Engagement Survey Canada in older persons with cancer
- Health status as measured by the EQ-5D in older persons with cancer and for family caregivers
- Health and social care services and resource use as measured by the Adapted Client Services Receipt Inventory in older persons with cancer
- Positive Aspects of Caregiving as measured by the Positive Aspects of Caregiving (PAC) questionnaire in family caregivers of older persons with cancer

Change from baseline at 48 weeks in the primary and secondary response variables.

- Time since randomization until death, in days, with censoring at 48 weeks after randomization

Study Methods

Trial design

- Multicentre (6 EU countries with 1 implementation site per country, except for Belgium (2 implementation sites) and the Netherlands (3 implementation sites)
- Pragmatic fast-track randomized controlled trial
- Superiority
- Parallel-group
- 1:1.08 allocation ratio (Control:Intervention) in Belgium (Flanders), Ireland, Italy, the Netherlands, and Portugal
- 1:1.45 allocation ratio (Control:Intervention) in Poland
- Non-blinded
- Partially nested design until week 24: patients in the intervention group are clustered within navigators, but patients in the control group are not (for the analysis of primary outcomes)
- Fully nested design from week 24 onwards

Interventions

Intervention = the NavCare-EU intervention plus care as usual

Patients allocated to the intervention group will immediately receive the NavCare-EU intervention plus care as usual for 48 weeks (12 months). The NavCare-EU intervention is a face-to-face and tele-

supported non-pharmacological intervention. The central component is a patient navigator, a dedicated person with or without a health-related background who engages with patients on an individual basis.

Navigators collaborate with patients and family caregivers throughout the continuum of supportive, palliative, and end-of-life care. Their main activities focus on addressing the needs, quality of life, and wellbeing of patients and family caregivers, the provision of information and psychosocial support, and ensuring people can connect to and access necessary services or resources. Every two weeks, navigators have face-to-face and/or telephone or IT-supported contact with patients and family carers, or in different intervals, as needed.

In the case of volunteers as navigator, expected caseload is one or two patients per navigator; in the case of professionals, a higher caseload per navigator is possible. The mean number of patients per navigator is expected to be 1.5 in Belgium (Flanders), Ireland, Italy, the Netherlands, and Portugal, and 10 patients in Poland.

Navigators are matched to patients and family carers by navigator coordinators. Navigators and coordinators are trained, coached, and mentored by a navigation trainer.

International trainers will aid country trainers to implement the intervention in their specific healthcare contexts and address country-generic and country-specific barriers and facilitators.

Control = care as usual

Patients allocated to the control group will first receive care as usual for six months (24 weeks) followed by the NavCare-EU intervention plus care as usual for 12 months (48 weeks).

- 2) The standard deviation of 25 points reflects the heterogeneity in the score at 6 months in EORTC QLQ-C30 in a similar usual care population (EORTC Quality of Life Group, 2008).
- 3) An ICC of 0.1 was chosen as a conservative estimate as there is currently no empirical data to support an exact estimate of the ICC.
- 4) A correlation between baseline and 24 weeks in baseline global health status/quality of life of 0.3 was chosen as a conservative estimate considering that correlations for longitudinal measures are very rarely below 0.5.
- 5) A drop-out of 50% is a more conservative estimate than those reported in the Nav-Care feasibility and pilot studies (35% over 1 year, 40% over 1 year, 17% over 6 months) ([name] et al, 2021; [name] et al, 2020; [name] et al, 2017). Moreover, the final analysis will include the available information from patients who drop out.
- 6) A significance level of 2.5% was chosen to control the Type I error rate, because the trial is designed so that two study endpoints could lead to a conclusion that effectiveness is established (Bonferroni correction).

We estimate an enrolment rate (patients enrolled out of all deemed eligible) of 55%. This includes an estimated 10% not being eligible because the family caregiver does not agree to participate, based on a palliative care pilot RCT in older people conducted by P1 VUB (de Nooijer et al 2021). This means we estimate to approach 151 patients per country in Belgium (Flanders), Ireland, Italy, the Netherlands, and Portugal to enrol 83 and 148 patients in Poland to enrol 81.

Framework

For all endpoints, the null hypothesis will be that there is no true difference between the NavCare-EU intervention and care as usual (superiority).

Statistical interim analyses and stopping guidance

No interim analyses to stop for efficacy or futility are planned.

Timing of final analysis

Analysis will take place in separate stages. First, the primary endpoints at week 24 will be analyzed. The subgroup analyses and the additional exploratory analyses (see further) will be performed at a later stage.

Figure 1 illustrates the timing of the schedules of enrolment, interventions, assessments, and participant visits. Data analyses will commence at least 6 months after completion of data collection per follow-up point, and we will aim to submit findings for publication within one year of starting data analysis.

[figure not shown]

Figure 1. Time schedule of enrolment, interventions, and assessments

Timing of outcome assessments

For the intervention group, outcomes will be measured at baseline (T0), 12 weeks (T1), 24 weeks (T2) and 48 weeks (T3) (see Figure 1). For the control group, outcomes will be measured at baseline (T0), 12 weeks (T1), 24 weeks (T2), 48 weeks (T3) and 72 weeks (T4).

Statistical Principles

Confidence intervals and P values

All hypothesis testing will be two-sided. The two primary endpoints will be tested at the 2.5% significance level (Bonferroni correction for multiplicity). The confidence intervals (CIs) for the estimated mean differences in the primary endpoints will be 97.5% CIs.

No adjustment for multiplicity will be made for other endpoints, as the results on these endpoints will only be interpreted after superiority on at least one of the primary endpoints can be demonstrated. Comparisons of secondary endpoints will be performed at the 5% significance level. Comparisons of exploratory endpoints and subgroup analyses should be considered as hypothesesgenerating (not conclusive) and interpreted with care.

All reported CIs (other than the ones for the estimated mean differences in the primary endpoints) will be 95% CIs.

Interpretation

The NavCare-EU intervention will be considered as beneficial if statistically significant and clinically relevant improvement compared with care as usual can be demonstrated on at least 1 of the 2 primary endpoints. Hence, NavCare-EU will be considered effective if the estimated effect on at least one of the endpoints is considered statistically significant (p < 0.025) and clinically relevant (≥10 points difference).

Analysis populations

All analysis will be performed on the intent-to-treat (ITT) population, which consists of all patients randomized. Subjects are analyzed according to the allocated intervention group irrespective of their compliance with the planned course of intervention. The ITT approach may reflect the effects of NavCare-EU on the different endpoints in daily practice.

Trial Population

Screening data

The total number of persons with cancer who are assessed for eligibility will be reported, together with reasons for not being willing to participate.

Eligibility

The inclusion and exclusion criteria are specified in the protocol. The number of ineligible persons with cancer randomized and the number of ineligible family caregivers included will be reported, together with reasons for ineligibility.

Recruitment

A CONSORT flow diagram will be used to summarize the number of persons with cancer who:

- gave informed consent
- were randomized
- received the allocated intervention
- did not receive the allocated intervention*
- lost to follow-up*
- discontinued the intervention*
- included in the primary analysis
- excluded from the primary analysis*

Withdrawal / Follow-up

Participants may withdraw from the intervention or from data collection. The PI can also discontinue a participant from the intervention in case of (1) significant study intervention non-adherence, (2) loss to follow-up, or (3) occurrence of an event, medical condition, or situation such that continued intervention would not be in the best interest of the participant. Reasons for discontinuing the intervention or data collection will be documented by the researcher/research assistant. In case participants only wish to withdraw from the intervention, they are invited to continue with data

^{*}reasons will be provided (e.g. withdrawal, death, etc).

collection, and priority will be given to collection of primary outcomes. Data collected after day of study withdrawal will not be used for analysis.

The numbers (with reasons) of withdrawals over the course of the trial will be summarized by treatment arm.

Baseline characteristics

Patient characteristics

- socio-demographic characteristics age, gender, country of birth, the country (ies) where the
 mother and father were born, highest educational level completed, whether the patient
 identifies with a specific religion or belief, with whom the patient currently lives,
 marital/partnership status, number of people that the patient consider to be important for
 them over the last 12 months and the extent to which the patient feels they can make ends
 meet (financial status).
- **clinical characteristics** organ or part of the body where the cancer was located and where it started, whether the cancer metastasized, age at diagnosis, comorbidities
- **functional status** Clinical Frailty Scale

Close family caregivers

socio-demographic characteristics – age (years), gender, country of birth, country(ies) where
the mother and father were born, highest educational level completed, whether the family
caregiver identifies with a specific religion or belief, , relation to the patient, whether they
live together with the patient, average number of hours spent with the patient during the
last week, average number of hours a week used to provide direct care to the patient, and
current employment status.

Using descriptive statistics, the characteristics of patients and their close family caregivers at baseline will be described and summarized, both for the control group and the intervention group. Continuous data will be summarised using mean and standard deviation (SD) if normally distributed, and median and 25th, 75th percentiles if not normally distributed. Categorical variables will be described using frequencies and percentages.

Analysis

Outcome definitions and derivations

We will use established and validated measures for all outcomes. Each outcome measure is a summary score of multiple items. Scores for global health / quality of life are computed if at least 50% of the items are valid (EORTC Quality of Life Group, 2001). Other summary scores are computed if at least 70% of the items are valid. In case of missing items, summary scores are the weighted sum of the observed items with weights inversely proportional to the number of valid items.

Analysis methods

All endpoints are continuous variables. We expect them to have a (log)normal distribution. Hence, linear mixed models (LMMs) for a normal distribution with identity link will be fitted. The random

effects part of the models will contain a random intercept for navigator and a random intercept for participant ID (patient ID / caregiver ID) nested within navigator for endpoints assessed in older persons with cancer / family caregivers respectively. The fixed effects part of the models will include group (intervention vs usual care), time point (post-intervention measurement at 24 weeks vs. baseline), their interaction group x time, and country (stratification factor for randomization). The interaction effect will capture the mean difference between groups in change from baseline. Estimated marginal means with corresponding CI will be reported.

Covariates

The FDA recommends adjusting for baseline covariates that are anticipated to be most strongly associated with the outcome of interest. Adjustment for these baseline covariates will generally reduce the variability of estimation of treatment effects and thus lead to narrower confidence intervals and more powerful hypothesis testing.

Because randomization is stratified by country, the models are adjusted for country. Otherwise, the standard error is likely to be overestimated and interval estimation and hypothesis testing can become unduly conservative.

For the analysis of the primary endpoint social support, as measured with the Medical Outcomes Study Social Support Survey (MOS), the model will include as covariate the older person's living situation, dichotomized as living alone vs not living alone.

No covariates are included in the analyses of the other primary endpoint.

Subgroup analyses

Subgroup analyses (led by the partner at University of Coimbra) will be performed (to explore the uniformity of the intervention effect compared with care as usual across on the primary and secondary endpoints. More information about the subgroup analyses and country comparative analysis plan will provided at a later time.

Missing data

Missing baseline characteristics

Missing values in the descriptive analysis of the baseline characteristics will be reported as missing. Missing baseline covariate data is assumed to be missing completely at random.

Missing outcome data

The LMM is fitted based on restricted maximum likelihood (REML). The analysis includes the available information from subjects with missing outcome values and yields valid inferences under the assumption that missing outcome data are missing at random (MAR). In our main analyses, we assume that missing outcome data can be related to the allocated intervention, baseline value of the outcome, and/or country, but that it is unrelated to other values. We will perform sensitivity analyses regarding the assumption behind the missing outcome data generating mechanism.

Sensitivity analyses

We will perform several sensitivity analyses for the primary endpoints, all regarding the assumption behind the missing data generating mechanism. In a first sensitivity analysis, we will make the MAR

assumption more plausible by including extra covariates (age category, functional status) in the fixed effects part of the LMM.

Given the expected dropout due to death, the MAR assumption might be too restrictive, therefore sensitivity analyses will be performed allowing a missing not at random (MNAR) mechanism. More specifically, starting from the MAR model, a jump-to-reference and tipping-point analysis will be applied. Additionally, another sensitivity analysis will be performed to deal with missingness due to death. We will estimate the effect of intervention among the unobservable subpopulation that would have survived under either arm (Chiba and VanderWeele, 2010). This is a conservative estimate of the intervention effect of interest.

Additional exploratory analyses

The control group will receive care as usual for six months (24 weeks), followed by the NavCare-EU intervention for 12 months (48 weeks). In this group, outcomes will also be assessed at 72 weeks from randomization, which corresponds to 48 weeks from the start of the intervention.

| Time since start of the intervention | Time since randomization | |
|--------------------------------------|--------------------------|---------------|
| | Intervention group | Control group |
| 0 weeks | 0 weeks | 24 weeks |
| 24 weeks | 24 weeks | 48 weeks |
| 48 weeks | 48 weeks | 72 weeks |

We will assess if receiving the NavCare-EU intervention 24 weeks after randomization is non-inferior to receiving the NavCare-EU intervention immediately after randomization, with respect to mean **change from start of the intervention** at 48 weeks in the primary and secondary endpoints. Similar LMMs as described for the main analyses will be fitted, but timepoints (week 48) will relate to the start of the intervention instead and not to randomization. A difference between groups less than 10 is considered not clinically relevant (non-inferiority margin).

Another additional exploratory objective is to assess mean differences over time in the primary and secondary endpoints. We will compare the estimated marginal mean responses (averaged over allocation groups) between timepoints (where timepoints relate to the start of the intervention and not to randomization).

Statistical software

Analyses will be conducted in R version 4.2.2 or more recent. The primary analyses will be repeated using SAS software (version 9.4 or more recent).

References

Chiba Y and Vanderweele T (2010) A Simple Method for Principal Strata Effects When the Outcome Has Been Truncated Due to Death. American Journal of Epidemiology.

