2.4 Monitoring

2.4.1 Data monitoring

An Ethical and Data Monitoring Board is created to monitor the intervention and data collection and any adverse events (see next section) will be reported to them. This Boards consists of an **Ethics Evaluator**, and the **independent trial monitors**. The primary role of the Ethical and Data Monitoring Board will be to periodically review the accumulating data and determine if the trial should be modified or discontinued.

An Ethics Evaluator external to the project will be appointed who will monitor the ethical aspects of the study, including data management and privacy concerns. This person (or team) will provide evaluation and advice on ethical, legal, data protection and data management issues based on an audit of the reporting by the different national trial managers to the Overall Trial Manager and the independent trial monitors in the different countries. This evaluation will be done shortly after the start of the trial study, and at least at three follow-up occasions.

The monitoring evaluations will be conducted by national independent trial monitors.

The following files are intended to guide data monitoring:

- The **Investigator Site File** will be held at each participating site. It contains copies of relevant global study documents and all original site-specific documents.
- The **Trial Master File will** be held at the coordinating site (VUB). It contains all original global study documents and a copy of all site-specific documents of all participating sites.

Both the Investigator Site File and the Trial Master File will include all essential documents for the trial as described in the ICH E6 Guideline for Good Clinical Practice (section 8) such as Initiation Meeting, Training Log & Handover Documents, Delegation of Authority Log, CV's/GCP Certificates, Final Protocol/Amendments, Protocol/Amendment Signature Page(s), Notifications to and Approval Letter(s) from Regulatory Authorities, Progress Reports, Informed Consent Forms Version Log and Signature Page(s), etc.

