- 2) A written protocol for addressing queries and distress will be provided to all researchers, navigators, navigator coordinators, data collectors and trial managers. Any serious adverse events should be reported in writing to the Principal Investigator and lead researcher in the respective country (if not identical to PI) within 24 hours of occurrence or identification. Unanticipated (but non-serious) adverse events will be reported to the PI within two working days. If neither the PI or lead researcher is available, the trial manager in the respective country will be contacted. If an adverse event is reported, the PI fills out a form about the event and will forward that information to the appropriate ethics committee in their country following the mechanisms for reporting these events. The PI will provide a judgment as to whether the adverse event is associated with or related to the study protocol. The PI will also contact the Ethical and Data Monitoring Review Board to report the adverse event and consult them regarding the need to revise the protocol to prevent a recurrence of the adverse event.
- 3) If the adverse event concerns emotional distress that cannot be addressed by the researchers (e.g. through pausing data collection and reassuring the participant) they will direct the participant to appropriate help, e.g. the patients' general practitioner or other community-based services.
- 4) Researchers will keep a log record of their communications with study participants which will allow us to document instances of distress and how they were addressed and managed.

Since the study involves older people with cancer and in deteriorating health, some patients may die due to disease progression, or related to other illnesses, but this would not be related to the study protocol. Only in the very unlikely event if this would occur during or immediately before or after a data collection appointment, or during the participant's travel to or from the research appointment, their death will be reported to the data monitoring committee (see previous section).

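### The SAP lists time to death as an endpoint, but its only analysis method is a linear mixed model that cannot handle it; a smaller point is that the rule on interpreting non-primary endpoints names no direction of effect

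*Combined protocol and SAP*

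**What the plan says.** **Time to death.** The SAP's list of exploratory endpoints ends with "Time since randomization until death, in days, with censoring at 48 weeks after randomization". Under Analysis methods the SAP states: "All endpoints are continuous variables. We expect them to have a (log)normal distribution". On that basis it fits normal linear mixed models with identity link. The fixed effects are group, "time point (post-intervention measurement at 24 weeks vs. baseline), their interaction group x time", and country. The random effects are intercepts for navigator and for participant within navigator. The treatment effect is the interaction, that is, the difference between arms in change from baseline. No other method is given for any endpoint.

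Under Interventions the SAP says: "Patients allocated to the control group will first receive care as usual for six months (24 weeks) followed by the NavCare-EU intervention". Under Withdrawal / Follow-up it excludes data collected after the day of study withdrawal.

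**Interpretation rule.** Under Confidence intervals and P values, all tests are two-sided. Each primary endpoint is tested at 2.5%, and other endpoints are left unadjusted because "results on these endpoints will only be interpreted after superiority on at least one of the primary endpoints can be demonstrated". Secondary endpoints (loneliness and caregiver burden) are tested at 5% with 95% intervals. The same paragraph then adds: "Comparisons of exploratory endpoints and subgroup analyses should be considered as hypothesesgenerating (not conclusive) and interpreted with care".

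**The concern.** The first issue is a stated analysis rule that fails for a listed endpoint. Mortality matters in this population: the sample size section expects 17.5% of patients to be lost through death, and this is the only planned comparison of mortality between arms. With no workable method in the SAP, the model, the horizon and the handling of withdrawals would be chosen after the deaths are known.

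The second issue is smaller. Making interpretation depend on a primary result protects against unsupported claims of benefit. It serves no such purpose for a difference favouring control, yet the sentence makes no distinction. If neither primary shows superiority, the authors would be told not to interpret an interval for caregiver burden lying wholly on the adverse side.

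**Working it through.** **1. Model against endpoint.**
- The model needs a baseline and a 24-week value for each participant. Time to death has one value and no baseline, so there is no change score and no group-by-time interaction to estimate.
- The model needs an observed, roughly normal or lognormal outcome. Time to death is unknown for everyone alive at 48 weeks or withdrawn. At the planning figures that is most patients.
- REML handles missing values as missing at random. A censored time is a lower bound, not a missing value.
- The survivor analysis under Sensitivity analyses treats death as a source of missing primary outcomes. It does not compare mortality.

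**2. What a week-24 mortality comparison could show.** The SAP plans 115 and 131 evaluable patients with 50% drop-out. 115/0.5 = 230 and 131/0.5 = 262, close to the stated 229 and 260 (total 489), which I use. I take the 17.5% mortality as applying by week 24, equal in both arms, and ignore clustering by navigator.
- Deaths: 0.175 × 229 = 40.1 and 0.175 × 260 = 45.5, total 85.6.
- SE of log hazard ratio: sqrt(1/40.1 + 1/45.5) = 0.217.
- 95% interval at a hazard ratio of 1.0: exp(±1.96 × 0.217) = 0.65 to 1.53.
- Hazard ratio detectable with 80% power at two-sided 5%: exp(2.80 × 0.217) = 1.83.
- If mortality were 10% or 25% (assumed range): about 49 or 122 deaths, upper limit 1.75 or 1.43.

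**3. The 48-week horizon.**
- At a constant hazard with vital status known for all: 1 − 0.825² = 31.9%, or 156 deaths; interval 0.73 to 1.37.
- With withdrawals censored, about half (244.5) remain at week 24. Applying 17.5% to them adds 42.8, giving 128 deaths; interval 0.71 to 1.41.
- Both arms receive NavCare-EU after week 24. A hazard ratio of 1.5 confined to weeks 0 to 24 (illustrative), with 39% of deaths falling later, averages exp(0.61 × ln 1.5) = 1.28 over 48 weeks.

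The longer horizon is more precise but answers a different question: immediate against deferred navigation.

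**4. How often the interpretation rule would apply.** First the plan's own figure.
- ANCOVA: 2 × (2.241 + 0.842)² × 25² × (1 − 0.3²)/10² gives 109 per arm, or 110 per arm (220 in total) with the t distribution, as stated.
- Clustering factors (1 + (m − 1) × 0.10)/0.90 are 1.167 for m = 1.5 and 2.111 for m = 10. Their square roots, 1.08 and 1.45, match the allocation ratios.
- With 246 evaluable patients split 5/6 and 1/6, the SE is 3.24 and power is Φ(10/3.24 − 2.241) = 80.1%.

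The rule would then withhold interpretation:
- at least 97.5% of the time with no true effect on either primary (1.25% favourable tail each);
- about 20% of the time with a true 10-point benefit on quality of life alone, under the planning ANCOVA.

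The SAP's actual group-by-time model is less efficient. With half retained and correlation 0.3, the weight on completers' baseline is 0.3 + 0.7 × 0.5 = 0.65. The variance factor is (1 + 0.65² − 2 × 0.65 × 0.3) + 0.35² = 1.155. Then SE = 25 × sqrt(1.155 × (1/115 + D/131)). D = 1.0 gives 3.43 and D = 5/6 × 1.167 + 1/6 × 2.111 = 1.32 gives 3.68. Power is 75% to 68%, so the rule applies 25% to 32% of the time.

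**5. What is withheld.** For caregiver burden, using the same correlation and retention, the 95% half-width is 1.96 × 3.43/25 = 0.27 SD if every patient has a participating caregiver and D = 1.0. It is 1.96 × 3.68/25 × sqrt(2) = 0.41 SD if half do and D = 1.32. The caregiver share is an assumption.

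**The case against.** **On time to death.** Analysis methods was plainly written for questionnaire scores: it describes every outcome as a summary of several items. The endpoint itself is defined in days with censoring, which is survival language. A reader might infer that the sponsor intends to model censored times linearly; the documents do not show that, and an oversight is more likely. The protocol also keeps analysts blind to arm, which limits the harm of a late choice. What stands is that the text covers all endpoints without exception and offers no alternative.

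A reader might also infer that week 24 should replace week 48. It need not. Immediate against deferred navigation is a legitimate intention-to-treat contrast in a fast-track design, 48 weeks is prespecified, and stopping at week 24 discards deaths.

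**On the interpretation rule.** This is conventional wording to justify unadjusted tests. A reader might infer that it also silences deaths, symptoms and emotional functioning. That is not shown: these are exploratory, and the same paragraph gives exploratory results their own rule, under which they are interpreted cautiously.

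Nor does harm go unseen. Adverse 95% intervals would be printed, both primaries are two-sided and outside the rule, and withdrawals with reasons are tabulated by arm. Adverse events go to a board that will "periodically review the accumulating data and determine if the trial should be modified or discontinued". That route does not fill the gap entirely. It plans no comparison between arms, and the Harms section sends a death to the committee "Only in the very unlikely event if this would occur during or immediately before or after a data collection appointment" or during travel to or from it. What remains of this half is the two secondary endpoints, chiefly caregiver burden.

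**Conclusion.** The main point holds on the text alone: time to death has no workable analysis in the SAP. The numbers show only what a proper analysis could deliver. About 86 deaths by week 24 would give an interval of roughly 0.65 to 1.53 around a hazard ratio of 1.0, so only a large difference could be detected. By week 48 there would be some 128 to 156 deaths, depending on how withdrawals are treated. These figures rest on the 17.5% planning mortality, equal hazards and no navigator clustering.

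The second point is a minor clarification. The rule is clear in its effect on caregiver burden and not shown to reach the exploratory endpoints. How often it would apply (20% to 32% in the case of a 10-point benefit on quality of life alone, at least 97.5% with no effect) is a property of any such rule and does not measure missed harm. The protocol expects at most mild distress, so little should turn on it.

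**What to change.** **Analysis methods.** State that time to death is excluded from the linear mixed model. It will be compared by randomised arm with Kaplan-Meier curves and a country-stratified Cox model at the stated 48-week horizon, censoring at study withdrawal. Report the week-24 contrast as well, before controls receive NavCare-EU, and note the low precision of both.

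**Confidence intervals and P values.** Add that the rule applies only to claims of benefit, and that adverse differences on secondary endpoints may be interpreted as unadjusted and not conclusive.

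**Cost.** Two short additions and one survival model. Sample size, alpha, power and type I error for benefit claims are unchanged. The protocol already has researchers document deaths. It describes no tracing of vital status after withdrawal, so censoring there assumes that withdrawal is unrelated to prognosis. With 32.5% expected to leave for other reasons, that assumption should be stated beside the withdrawals already tabulated by arm. Opening the two secondary endpoints to adverse readings brings some false alarms: with no true effect, the chance of at least one nominally significant adverse difference is 1 − 0.975² = 4.9% if they are independent, and never more than 5%. The label of not conclusive deals with that.
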